9.2. Definition of Serious Adverse Event

If an event is not an AE per definition above, then it cannot be an SAE even if serious conditions are met (eg, hospitalization for signs/symptoms of the disease under study, death due to progression of disease).

A Serious Adverse Event is defined as any untoward medical occurrence that, at any dose:

a. Results in death

b. Is life-threatening

The term 'life-threatening' in the definition of 'serious' refers to an adverse drug experience that places the participant, in the opinion of the initial reporter, at immediate risk of death from the adverse experience as it occurred. This does not include an adverse drug experience that, had it occurred in a more severe form, might have caused death.

c. Requires inpatient hospitalization or prolongation of existing hospitalization

In general, hospitalization signifies that the participant has been detained (usually involving at least an overnight stay) at the hospital or emergency ward for observation and/or treatment that would not have been appropriate in the physician's office or outpatient setting. Complications that occur during hospitalization are AEs. If a complication prolongs hospitalization or fulfills any other serious criteria, the event is serious. When in doubt as to whether "hospitalization" occurred or was necessary, the AE should be considered serious.

Hospitalization for elective treatment or planned surgery (eg, stent replacement, hip surgery) is not considered an SAE.

Hospitalization for medical interventions in which no unfavorable medical occurrence occurred (ie, elective procedures or routine medical visits) is not considered an SAE.

d. Results in persistent or significant disability/incapacity

- The term disability means a substantial disruption of a person's ability to conduct normal life functions.
- This definition is not intended to include experiences of relatively minor medical significance, such as uncomplicated headache, nausea, vomiting, diarrhea, influenza, and accidental trauma (eg, sprained ankle), that may interfere with or prevent everyday life functions but do not constitute a substantial disruption.

e. Is a congenital anomaly/birth defect

f. Other situations (Important Medical Event)

An event that may not result in death, be immediately life-threatening, or require hospitalization, but may be considered serious when, based on appropriate medical judgment, the event may jeopardize the participant and may require medical or surgical intervention to prevent one of the outcomes listed in the above definition. Examples of such events include invasive or malignant cancers (excluding the disease[s] under study in oncology protocols), intensive treatment in an emergency department or at home for allergic bronchospasm, blood dyscrasias, or convulsions that do not result in hospitalization, or development of drug dependency or drug abuse.

9.3. Recording and Follow-Up of Adverse Events and/or Serious Adverse Events

Adverse Event and Serious Adverse Event Recording

- An AE/SAE that begins or worsens after informed consent is signed should be recorded on the Adverse Event Form in the eCRF. Conditions that were present at the time informed consent was given should be recorded on the Medical History Form in the eCRF.
- When an AE/SAE occurs, it is the responsibility of the investigator to review all documentation (eg, hospital progress notes, laboratory reports, and diagnostics reports) related to the event.
- The investigator (or delegate) will then record all relevant AE/SAE information in the eCRF.
- It is **not** acceptable for the investigator to send photocopies of the participant's medical records in lieu of completing the AE eCRF page.
- There may be instances when copies of medical records for certain cases are requested. In this case, all participant identifiers, with the exception of the participant number, will be redacted on the copies of the medical records before submission.
- The investigator will attempt to establish a diagnosis of the event based on signs, symptoms, and/or other clinical information. Whenever possible, the diagnosis (not the individual signs/symptoms) will be documented as the AE/SAE. When a clear diagnosis cannot be identified, each sign or symptom should be reported as a separate AE/SAE.

To the extent possible, each AE/SAE should be evaluated to determine:

- The severity grade (CTCAE Grade 1 to 5). See below for further instructions on the assessment of intensity.
- Whether there is at least a reasonable possibility that the AE is related to the study treatment (including itacitinib(s) and/or reference therapy): suspected (yes) or not suspected (no). See below for further instructions on the assessment of causality.
- The start and end dates, unless unresolved at final follow-up.
- The action taken with regard to study treatment as a result of the AE/SAE(s) and/or reference therapy.
- The event outcome (eg, not recovered/not resolved, recovered/resolved, recovering/resolving, recovered/resolved with sequelae, fatal, unknown).
- The seriousness, as per the SAE definition provided in Section 9.2.
- The action taken with regard to the event. Note: If an AE is treated with a concomitant medication or nondrug therapy, this action should be recorded on Adverse Event Form and the treatment should be specified on the appropriate eCRF (eg, Prior/Concomitant Medications, Procedures and Non-Drug Therapy).

Assessment of Intensity

The severity of AEs will be assessed using CTCAE v5.0 Grades 1 through 5. For the purposes of this Protocol, CRS and ICAN events will be graded per ASBMT CRS Consensus Grading and ASBMT ICANs Consensus Grading, respectively. If an event is not classified by CTCAE, the severity of the AE will be graded according to the scale below to estimate the grade of severity:

The investigator will make an assessment of intensity for each AE and SAE reported during the study and assign it to 1 of the following categories:

- **Grade 1:** Mild; asymptomatic or mild symptoms; clinical or diagnostic observations only; treatment not indicated.
- **Grade 2:** Moderate; minimal, local, or noninvasive treatment indicated; limiting age appropriate activities of daily living.
- **Grade 3:** Severe or medically significant but not immediately life-threatening; hospitalization or prolongation of hospitalization indicated; disabling; limiting self-care activities of daily living.
- **Grade 4:** Life-threatening consequences; urgent treatment indicated.
- **Grade 5:** Fatal.

Assessment of Causality

- The investigator is obligated to assess the relationship between study treatment and each occurrence of each AE/SAE. If reference therapy is used in combination with an Incyte itacitinib, the relationship to each itacitinib/reference therapy must be assessed (ie, for the Incyte product(s) and for the other product(s) that is used in combination with the Incyte product). If appropriate, the relationship to the combination may be assessed as well.
- A "reasonable possibility" of a relationship conveys that there are facts, evidence, and/or arguments to suggest a causal relationship, rather than that a relationship cannot be ruled out.
- The investigator will use clinical judgment to determine the relationship.
- The investigator will also consult the Reference Safety Information in the IB and/or Product Information, for marketed products, in his/her assessment.
- Alternative causes, such as underlying disease(s), concomitant therapy, and other risk factors, as well as the temporal relationship of the event to study treatment administration, will be considered and investigated.
- For each AE/SAE, the investigator **must** document in the medical notes that he/she has reviewed the AE/SAE and has provided an assessment of causality.
- With regard to assessing causality of SAEs:
 - There may be situations in which an SAE has occurred and the investigator has minimal information to include in the initial report. However, the causality assessment is one of the criteria used when determining regulatory reporting requirements. **Therefore, it is very important that the investigator always make an assessment of causality for every event before the initial transmission of the SAE.**
 - The investigator may change his/her opinion of causality in light of follow-up information and send a follow-up SAE report with the updated causality assessment.

Follow-Up of Adverse Events and Serious Adverse Events

- The investigator is obligated to perform or arrange for the conduct of supplemental measurements and/or evaluations as medically indicated or as requested by the sponsor to elucidate the nature and/or causality of the AE or SAE as fully as possible. This may include additional laboratory tests or investigations, histopathological examinations, or consultation with other health care professionals.
- New or updated information will be recorded in the originally completed eCRF.
- Any updated SAE data will be submitted to the sponsor (or designee) within 24 hours of receipt of the information.
- Once an AE is detected, it should be followed until it has resolved or until it is judged to be permanent; assessment should be made at each visit (or more frequently if necessary) of any changes in severity, the suspected relationship to the study treatment, the interventions required to treat the event, and the outcome.
- When the severity of an AE changes over time for a reporting period (eg, between visits), each change in severity will be reported as a separate AE until the event resolves.

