10.4.3.1. Adverse Events

Adverse events will be coded by the Medical Dictionary for Regulatory Activities dictionary, and TEAEs (ie, AEs reported for the first time or worsening of a pre-existing event after first dose of study treatment) will be tabulated by preferred term and system organ class for all events, related events, and events of Grade 3 or higher.

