9.2. Adverse Events

9.2.1. Adverse Event Definitions

A TEAE is any AE either reported for the first time or worsening of a pre-existing event after the first dose of study drug. Analysis of AEs (as discussed below) will be limited to TEAEs, but data listings will include all AEs regardless of their timing in relation to study drug administration.

Adverse events will be tabulated by MedDRA PT and SOC. Severity of AEs will be graded using the NCI CTCAE v5.0. The CTCAE reporting guidelines and grading details are available on the Cancer Therapy Evaluation Program website.

The subset of AEs considered by the investigator to be related to study drug will be considered to be treatment-related AEs. If the investigator does not specify the relationship of the AE to study drug, the AE will be considered to be treatment-related. The incidence of AEs and treatment-related AEs will be tabulated.

In addition, serious TEAEs will also be tabulated.

Any missing onset date, causality, or severity must be queried for resolution. Unresolved missing causality and severity will be handled according to the following rules:

- An unresolved missing causality will be considered treatment-related.
- An unresolved missing severity will be identified as an unknown severity.

For purposes of analysis, all AEs will be considered TEAEs unless the AE can unequivocally be defined as not treatment-emergent.

- If the stop/resolution date is before the first dose administration date on Day 1, then the AE will be considered as not being treatment-emergent.
- If both the month and day are missing, and the last day of the year is before the first dose administration date on Day 1, then the AE will not be considered treatment-emergent.

- If only the day is missing, and the last day of the month is before the first dose administration date on Day 1, then the AE will not be considered treatment-emergent.
- If only the day is missing, and the first day of the month is after the first dose administration date on Day 1, then the AE will be considered treatment-emergent.

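### A pre-dose adverse event that improves after first dose can be counted as treatment-emergent, because the SAP neither links its severity records nor compares their grades

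*Protocol*

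**What the plan says.** **Recording (Protocol 9.3).** Entry to the AE form starts at consent: "An AE/SAE that begins or worsens after informed consent is signed should be recorded on the Adverse Event Form in the eCRF". Conditions already there go elsewhere: "Conditions that were present at the time informed consent was given should be recorded on the Medical History Form in the eCRF". Once an event is on the form and its severity changes, "each change in severity will be reported as a separate AE until the event resolves". A neighbouring item in the same list says: "New or updated information will be recorded in the originally completed eCRF". Neither sentence says whether a fall in grade opens a new record.

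**Definition (SAP 9.2.1 and Protocol 10.4.3.1).** The SAP states: "A TEAE is any AE either reported for the first time or worsening of a pre-existing event after the first dose of study drug". The protocol agrees: "AEs reported for the first time or worsening of a pre-existing event after first dose of study treatment".

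**Working rule (SAP 9.2.1).** The same section then says that "all AEs will be considered TEAEs unless the AE can unequivocally be defined as not treatment-emergent". Four date rules follow. Three exclude: a stop date before first dose, a date with month and day missing whose year ended before first dose, and a date with only the day missing whose month ended before first dose. The fourth includes: a date with only the day missing whose month begins after first dose. None uses the grade, and none ties a severity-change record to the record before it.

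**Reporting.** SAP 4.1.7 puts safety data collected after Day 1, which SAP 4.1.3 defines as the first-dose date, into the summary tables. SAP 9.2.2 counts participants with any TEAE, with Grade 3 or higher TEAEs, and by preferred term.

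**The concern.** Screening runs from Day -17 to Day -4 and the first dose is on Day -3 (Protocol Table 3), so AEs can be recorded for up to 14 days before dosing. If such an event is still ongoing at first dose and then eases, a literal reading of Protocol 9.3 opens a new record that starts after first dose. The SAP presumption takes that record in, and no listed exclusion takes it out. A participant who is recovering would then appear in the tables as having had a treatment-emergent event. A fall from Grade 4 to Grade 3 would enter the Grade 3 or higher tables in the same way.

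This matters because Protocol 10.4.3 uses safety summaries across the two dose groups and placebo to help confirm the choice of dose. With arms of about 23, a few such participants would visibly change the rate for a single term.

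**Working it through.** The plan gives no figure to reproduce. The check is a classification exercise, followed by simple arithmetic on scale.

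**Step 1: a test case.** Take a hypothetical participant with complete dates. A Grade 3 AE starts after consent and 5 days before first dose. It improves to Grade 2 four days after first dose and resolves nine days after first dose. Assume that the first record closes when the grade changes and a second then opens, as Protocol 9.3 reads literally. As a contrast, let the second record be a worsening to Grade 4 on the same dates.

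**Step 2: classify each record in three ways.** First by the SAP date rules alone, where a fully dated record is excluded only if it stops before first dose. Then by the TEAE definition with consecutive records linked. Then by the definition with each record standing as its own AE.

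| Record | Date rules alone | Definition, linked | Definition, unlinked |
|---|---|---|---|
| Original Grade 3, starts before first dose | TEAE | not TEAE | not TEAE |
| Step-down to Grade 2, starts after first dose | TEAE | not TEAE | TEAE |
| Contrast: step-up to Grade 4, starts after first dose | TEAE | TEAE | TEAE |

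The step-down record is kept out only when records are linked and grades compared, which neither document asks for. The worsening record is a TEAE in every column, so linking loses nothing there.

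The first row carries a second lesson. By the date rules alone even the original record is a TEAE, because it stops after first dose. Those rules therefore cannot be the whole test without contradicting the definition in the same section. Screening on onset date would remove the original record but not the step-down, whose onset is after first dose.

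**Step 3: scale.** The inputs are the planned sizes: 23 per arm in Part 2 and 62 in Part 1 (Protocol 10.1, SAP 3.4). One participant counted wrongly adds

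- Part 2: 1/23 = 4.3 percentage points to that arm;
- Part 1: 1/62 = 1.6 percentage points.

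This applies to a table row in which the participant has no other qualifying TEAE. The sizes are for the efficacy evaluable set. The safety population also includes participants who were dosed but received no cell therapy, so it may be somewhat larger and the increments somewhat smaller.

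**The case against.** The strongest reply is that the definition already settles the case. An improving pre-dose event is neither new nor worse, the list of date rules is nowhere called exhaustive, and with known dates and grades such an event can be shown not to be treatment-emergent. That is right once records are linked. But Protocol 9.3 calls the new record a separate AE, the SAP does not say to link it to its parent, and an unlinked record looks like a first report after dosing. The correct result depends on a step that is not written down.

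A second reply is that improvement may not open a new record at all. Protocol 9.3 does not state the direction of change, the entry rule speaks of events that begin or worsen, and updates are to go in the original form. This stands in part. The entry rule governs how an event first reaches the form and the severity rule governs what follows, but the wording can be read either way. A reader might infer that the protocol expressly records every improvement as a new AE, or that the SAP always counts it. The documents support only that it can happen.

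A third reply concerns scope, and it stands. Conditions present at consent are outside this route. Exclusion criterion 7 removes most unresolved toxicity of Grade 2 or higher from earlier anticancer therapy. Conditioning chemotherapy is given at the investigator's discretion with no dates stated, so the documents do not show that its toxicities are easing rather than worsening after Day -3. For cytopenias, the laboratory shift tables (SAP 9.4.2) and the tables of treatment-emergent laboratory worsening (SAP Appendix A) give a view relative to baseline, although they do not correct the AE tables.

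**Conclusion.** The point holds as a gap between two stated rules. The recording rule and the TEAE presumption together can turn recovery from a pre-dose AE into a treatment-emergent event, against the SAP's own definition. It is confined to AEs that begin between consent and first dose, are ongoing at first dose and then improve, and it assumes that sites open a new record when the grade falls.

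The total effect cannot be computed. The documents do not say how many participants meet these conditions, and the number could be close to zero; only the per-participant increments are firm. A reader might go further and infer that Part 1 TEAE rates are overstated, or that background recovery shrinks the Part 2 safety contrast by a known amount. Either would require an assumed share of affected participants that has no source in the protocol or SAP.

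The gap is still worth closing before database lock, because the remedy is small and the AE tables feed dose selection.

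**What to change.** Add to SAP 9.2.1, after the TEAE presumption:

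> Consecutive records of one continuous event are linked. If the event began before the first dose of study drug, a post-dose record is treatment-emergent only if its grade exceeds the last grade recorded before the first dose, or exceeds a lower grade reached after the first dose (re-worsening).

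The reference should be the last pre-dose grade, not the highest. Suppose an event is Grade 3 in screening, Grade 1 at first dose and Grade 3 again on study drug. Against the highest pre-dose grade, 3 does not exceed 3 and a true worsening is lost. Against the last, 3 exceeds 1 and it is kept. The last-value choice also agrees with the safety baseline in SAP 4.1.5. The re-worsening clause keeps an event that eases after first dose and then worsens again.

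In the test case, the Grade 2 step-down is not a TEAE (2 does not exceed 3) and the Grade 4 step-up is (4 exceeds 3).

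The Protocol 9.3 recording rule can stay as it is. No new data are needed, since grade and start and end dates are already collected. The cost is a record-linking step in the AE dataset and slightly lower TEAE counts.

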9.4. Reporting of Serious Adverse Events

Regardless of suspected causality (eg, relationship to study treatment[s], reference therapy, or study procedure[s]), all SAEs occurring after the participant has signed the ICF through the last study visit or at least 30 days after the last dose of study treatment must be reported to the sponsor (or designee) within **24 hours** of learning of its occurrence, unless otherwise specified by the Protocol. If an SAE occurs more than 30 days after the last dose of study treatment, it is only required to be reported if it is considered to be related to study treatment. The investigator will submit any updated SAE data to the sponsor (or designee) within 24 hours of it being available.

Investigators are not obligated to actively seek SAE information after conclusion of the study participation. However, if the investigator learns of any SAE, including a death, at any time after a participant has been discharged from the study, and he/she considers the event to be reasonably related to the study treatment or study participation, the investigator must notify the sponsor (or designee) within 24 hours of becoming aware of the event.

After the initial AE/SAE report, the investigator is required to proactively follow each participant at subsequent visits/contacts. All SAEs, will be followed until resolution, stabilization, the event is otherwise explained, or the participant is lost to follow-up (see Section [7.3](#)).

Prompt notification by the investigator to the sponsor of a SAE is essential so that legal obligations and ethical responsibilities towards the safety of participants and the safety of a study treatment under clinical investigation are met.

If the SAE is not documented in the [IB](#) for the study treatment (new occurrence) and is thought to be related to the study treatment, the sponsor or its designee may urgently require further information from the investigator for reporting to health authorities. The sponsor or its designee may need to issue an Investigator Notification to inform all investigators involved in any study with the same drug that this SAE has been reported. Suspected Unexpected Serious Adverse Reactions will be collected and reported to the competent authorities and relevant ethics

committees in accordance with Directive 2001/20/EC, or as per national regulatory requirements in participating countries.

The sponsor has a legal responsibility to notify both the local regulatory authority and other regulatory agencies about the safety of a study treatment under clinical investigation. The sponsor will comply with country-specific regulatory requirements relating to safety reporting to the regulatory authority, IRB, and investigators.

Investigator safety reports must be prepared for suspected unexpected serious adverse reactions according to local regulatory requirements and sponsor policy and forwarded to investigators as necessary.

An investigator who receives an investigator safety report describing a SAE or other specific safety information (eg, summary or listing of SAEs) from the sponsor will review and then file it along with the IB and will notify the IRB, if appropriate according to local requirements.

Serious Adverse Event Reporting

- Information about all SAEs is collected and recorded on the Adverse Event Form in the eCRF.
- The investigator must report within 24 hours of learning of its occurrence any SAE by completing the Serious Adverse Event Report Form in English.
- Follow-up information is recorded on an amended or new Serious Adverse Event Report Form, with an indication that it is follow-up to the previously reported SAE and the date of the original report. The follow-up report should include information that was not provided on the previous Serious Adverse Event Report Form, such as the outcome of the event (eg, resolved or ongoing), treatment provided, action taken with study treatment because of the SAE (eg, dose reduced, interrupted, or discontinued), or participant disposition (eg, continued or withdrew from study participation). Each recurrence, complication, or progression of the original event should be reported as follow-up to that event, regardless of when it occurs.
- Contacts for SAE reporting can be found in the investigator site file.

